15.4 Publication, Disclosure, and Clinical Trial Registration Policy

15.4.1 Publication and Disclosure

The results of this trial are expected to be published in a scientific journal. It is anticipated that clinical and laboratory co-Investigators will participate in authorship. The order of authorship and choice of journal will be determined by the PIs and the Sponsor. The data analysis center for this trial will provide the analyses needed for publication. Information regarding this trial will be posted on ClinicalTrials.gov.

15.4.2 Clinical Trial Registration

In order to ensure that information on clinical trials reaches the public in a timely manner and to comply with applicable law, regulation and guidance, the Sponsor will, at a minimum register all clinical trials conducted in subjects that it sponsors anywhere in the world on ClinicalTrials.gov or other publicly accessible websites before trial initiation. The Sponsor contact information, along with Investigator's city, country, and recruiting status will be registered and available for public viewing.

CONFIDENTIAL

15.4.3 Clinical Trial Results Disclosure

The Sponsor will post the results of this clinical trial, regardless of outcome, on ClinicalTrials.gov or other publicly accessible websites, as required by applicable laws and/or regulations.

Trial completion corresponds to the date on which the final subject was examined or received an intervention for the purposes of final collection of data for the primary outcome, whether the clinical trial concluded according to the pre-specified protocol or was terminated.

15.5 Insurance and Compensation for Injury

Each subject in the trial must be insured in accordance with the regulations applicable to the site where the subject is participating. If a local underwriter is required, then the Sponsor or Sponsor's designee will obtain clinical trial insurance against the risk of injury to clinical trial subjects. Refer to the Clinical Study Site Agreement regarding the Sponsor's policy on subject compensation and treatment for injury. If the Investigator has questions regarding this policy, he or she should contact the Sponsor or Sponsor's designee.

CONFIDENTIAL

Appendix A Responsibilities of the Investigator

Clinical research studies sponsored by the Sponsor are subject to ICH GCP and all the applicable local laws and regulations.

The Investigator agrees to assume the following responsibilities:

1. Conduct the trial in accordance with the protocol.
2. Personally conduct or supervise the staff who will assist in the protocol.
3. Ensure that trial related procedures, including trial specific (non-routine/non-standard panel) screening assessments are NOT performed on potential subjects, prior to the receipt of written approval from relevant governing bodies/authorities.
4. Ensure that all colleagues and employees assisting in the conduct of the trial are informed of these obligations.
5. Secure prior approval of the trial and any changes by an appropriate IRB/IEC that conform to ICH and local regulatory requirements.
6. Ensure that the IRB/IEC will be responsible for initial review, continuing review, and approval of the protocol. Promptly report to the IRB/IEC all changes in research activity and all anticipated risks to subjects. Make at least yearly reports on the progress of the trial to the IRB/IEC, and issue a final report within 3 months of trial completion.
7. Ensure that requirements for informed consent, as outlined in ICH and local regulations, are met.
8. Obtain valid informed consent from each subject who participates in the trial, and document the date of consent in the subject's medical chart. Valid informed consent is the most current version approved by the IRB/IEC. Each informed consent form should contain a subject authorization section that describes the uses and disclosures of a subject's personal information (including personal health information) that will take place in connection with the trial. If an informed consent form does not include such a subject authorization, then the Investigator must obtain a separate subject authorization form from each subject or the subject's legally acceptable representative.
9. Prepare and maintain adequate case histories of all persons entered into the trial, including eCRFs, hospital records, laboratory results, etc., and maintain these data for a minimum of 2 years following notification by the Sponsor that all investigations have been discontinued or that the regulatory authority has approved the marketing application. The Investigator should contact and receive written approval from the Sponsor before disposing of any such documents.
10. Allow possible inspection and copying by the regulatory authority of GCP-specified essential documents.

CONFIDENTIAL

11. Maintain current records of the receipt, administration, and disposition of Sponsor-supplied vaccines, and return all unused Sponsor-supplied vaccines to the Sponsor.
12. Report AEs to the Sponsor promptly. In the event of an SAE, notify the Sponsor within 24 hours.

CONFIDENTIAL

Appendix B Investigator Consent to Use of Personal Information

Takeda will collect and retain personal information of Investigator, including his or her name, address, and other personally identifiable information. In addition, Investigator's personal information may be transferred to other parties located in countries throughout the world (e.g., the United Kingdom, United States, and Japan), including the following:

- Takeda, its affiliates, and licensing partners.
- Business partners assisting Takeda, its affiliates, and licensing partners.
- Regulatory agencies and other health authorities.
- IRBs and IECs.

Investigator's personal information may be retained, processed, and transferred by Takeda and these other parties for research purposes including the following:

- Assessment of the suitability of Investigator for the trial and/or other clinical studies.
- Management, monitoring, inspection, and audit of the trial.
- Analysis, review, and verification of the trial results.
- Safety reporting and pharmacovigilance relating to the trial.
- Preparation and submission of regulatory filings, correspondence, and communications to regulatory agencies relating to the trial.
- Preparation and submission of regulatory filings, correspondence, and communications to regulatory agencies relating to other vaccines used in other clinical studies that may contain the same chemical compound present in the investigational vaccine.
- Inspections and investigations by regulatory authorities relating to the trial.
- Self-inspection and internal audit within Takeda, its affiliates, and licensing partners.
- Archiving and audit of trial records.
- Posting Investigator site contact information, trial details and results on publicly accessible clinical trial registries, databases, and websites.

Investigator's personal information may be transferred to other countries that do not have data protection laws that offer the same level of protection as data protection laws in Investigator's own country. Investigator acknowledges and consents to the use of his or her personal information by Takeda and other parties for the purposes described above.

CONFIDENTIAL

3.0 LIST OF ABBREVIATIONS

AE	Adverse Event
BMI	Body Mass Index
CMI	Cell-mediated Immunity
DEN	Dengue Virus
DENV	Dengue Virus (wild type)
DHF	Dengue Hemorrhagic Fever
DSS	Dengue Shock Syndrome
E	Envelope
ELISA	Enzyme-linked immunosorbent assay
eCRF	electronic Case Report Form
FAS	Full Analysis Set
FDA	Food and Drug Administration
GCP	Good Clinical Practice
GMT	Geometric Mean Titer
HD-TDV	High dose TDV formulation
HCV	Hepatitis C Virus
HIV	Human immunodeficiency virus
IB	Investigator Brochure
ICH	International Conference on Harmonization
IEC	Independent Ethics Committee
Ig	Immunoglobulin
Inc	Incorporated
IRB	Institutional Review Board
IUD	Intrauterine device
IWRS	Interactive Web Response System
MedDRA	Medical Dictionary for Regulatory Activities
MNT	Microneutralization test
CCI	[REDACTED]
PBMC(s)	Peripheral Blood Mononuclear Cells

PFU	Plaque Forming Units
PPS	Per-Protocol Set
prM	pre-membrane
PT	Preferred term
RNA	Ribonucleic Acid
SAE	Serious Adverse Event
SC	Subcutaneous
SOC	System Organ Class
SOP	Standard operating procedures
SUSAR	Suspected Unexpected Serious Adverse Reaction
TDV	Tetravalent Dengue Vaccine Candidate
US	United States
WHO	World Health Organization

4.0 OBJECTIVES

4.1 Primary Objective

- To assess the post-vaccination neutralizing antibody response against each dengue serotype by vaccine group.

4.2 Secondary Objectives

Safety:

- To assess the safety of HD-TDV and TDV by vaccine group and baseline dengue seropositivity (MNT).

Immunogenicity:

- To assess the post-vaccination neutralizing antibody response against each dengue serotype by vaccine group and baseline dengue seropositivity (MNT).

Vaccine viremia:

- To assess vaccine viremia post-vaccination by vaccine group and baseline dengue seropositivity (MNT).

4.3 Exploratory Objectives

- **CCI**
[REDACTED]
- To characterize humoral immune response.
- To characterize cell-mediated immunity in the CMI subset.

[figure not shown]
4.4 Trial Design

This is a descriptive, Phase II, double-blind, randomized, and controlled trial in 400 subjects aged 21 to 45 years living in Singapore. Subjects will be randomized (1:1) into two vaccine groups:

- Arm 1 will receive one subcutaneous (SC) dose of HD-TDV;
- Arm 2 will receive one SC dose of TDV.

Randomization will be stratified based on the dengue IgG status (positive/negative) at screening, resulting in four investigational groups ([Figure 4.a](#)).

Figure 4.a Schematic Showing the Stratified Randomization Process

[figure not shown]

(a) Approximately 40 subjects in each of the IgG positive and negative groups will form the CMI subset.

Subjects will be followed for one year, with 13 scheduled visits, for the assessment of reactogenicity, safety and/or immunogenicity (Figure 4.b). Cell-mediated immunity will be assessed in a subset of approximately 80 subjects (approximately 40 subjects in each of the IgG positive and negative groups). This CMI subset will consist of volunteers identified at the time of randomization.

The duration of the study for each subject will be approximately 365 days (12 months) following vaccination on Day 1 (Month 0). An interim analysis is planned on cleaned data up to 6 months post-vaccination to provide data to support the planning and execution of other studies in the development plan of TDV.

Figure 4.b Schematic Showing Subject Flow through the Trial

Immunogenicity evaluation:

Neutralizing antibodies (MNT) will be measured on blood samples collected pre-vaccination on Day 1 (Month 0) and post-vaccination on Days 15, 30 (Month 1), 90 (Month 3), 180 (Month 6) and 365 (Month 12).

Assessment of viral replication:

Vaccine viremia will be assessed on blood samples collected pre-vaccination on Day 1 (Month 0) and post-vaccination on Days 5, 7, 9, 11, 15, 17, 21 and 30 (Month 1).

[figure not shown]
Safety evaluation:

Subjects will be provided with a diary card for the recording of:

- Solicited local AEs for 7 days following vaccination (day of vaccination + 6 days). These will include: injection site pain, injection site erythema, and injection site swelling.
- Solicited systemic AEs for 14 days following vaccination (day of vaccination + 13 days). These will include: fever, headache, asthenia, malaise, and myalgia.
- Unsolicited AEs for 28 days following vaccination (day of vaccination + 27 subsequent days).
- Serious adverse events throughout the trial.

Exploratory assessments:

CCI

Neutralizing and non-neutralizing antibodies will be characterized on blood samples collected pre-vaccination on Day 1 (Month 0), and post-vaccination on Days 30 (Month 1), 60 (Month 2), 90 (Month 3), 180 (Month 6) and 365 (Month 12) by different exploratory assays.

CMI will be assessed in a subset of subjects on blood samples collected pre-vaccination on Day 1 (Month 0), and post-vaccination on Days 30 (Month 1), 60 (Month 2), 90 (Month 3), 180 (Month 6) and 365 (Month 12).

5.0 ANALYSIS ENDPOINTS

5.1 Primary Endpoints

- Geometric mean titers (GMTs) of neutralizing antibodies for each of the four dengue serotypes post-vaccination on Days 15, 30 (Month 1), 90 (Month 3), 180 (Month 6), 365 (Month 12).
- Seropositivity rates (% of subjects) for each of the four dengue serotypes post-vaccination on Days 15, 30 (Month 1), 90 (Month 3), 180 (Month 6), 365 (Month 12) where seropositivity is defined as a reciprocal neutralizing titer ≥ 10 .

5.2 Secondary Endpoints

Safety

- Frequency and severity of solicited local (injection site) adverse events (AEs) for 7 days and solicited systemic AEs for 14 days after vaccination.
- Percentage of subjects with any unsolicited AEs for 28 days after vaccination.
- Percentage of subjects with serious adverse events (SAEs) throughout the trial.

Immunogenicity

- Refer to primary endpoints, but will be analyzed by dengue baseline seropositivity status (seropositive for at least 1 dengue serotype/seronegative for all dengue serotypes).

Vaccine viremia

- Incidence, duration, and level of vaccine viremia for each of the four dengue serotypes post-vaccination.

5.3 Exploratory Endpoints

- **CC1**
[REDACTED]
- Additional analyses will be performed to characterize humoral immune response and cell-mediated immune response (CMI subset).

6.0 DETERMINATION OF SAMPLE SIZE

As this study is descriptive and is not based on testing formal null hypotheses, the sample size was not determined based on formal statistical power calculations. The sample size was considered sufficient to meet the endpoints of the study.

7.0 METHODS OF ANALYSIS AND PRESENTATION

7.1 General Considerations

This Statistical Analysis Plan (SAP) was developed based on International Conference on Harmonization E3 [1] and E9 [2] Guidelines, and information provided in Protocol DEN-205, Version 3.0 dated 25 April 2017 [3].

All statistical analyses will be generated using SAS Version 9.2 or higher.

This document will provide the details regarding the definition of analysis variables and analysis methodology to address all study objectives. No inferential analyses will be performed for this study, i.e. all analyses described in this SAP will be exploratory only.

A blinded data review will be conducted prior to unblinding of subject's vaccination assignment. This review will assess the accuracy and completeness of the study database, subject evaluability, and appropriateness of the planned statistical methods.

7.1.1 Data Presentation

Immunogenicity, vaccine viremia, and safety endpoints will be summarized descriptively (frequency and percent for categorical data; and number of subjects with non-missing observation, mean, standard deviation (SD), median, minimum and maximum for continuous data) by all relevant study visits, if appropriate. In summary tables for categorical data for which categories are defined on the eCRF, all categories will be presented as specified, even if the subject count within that category is zero. For other categorical data (e.g. AEs and medications), only categories with at least one subject will be presented.

Minimum and maximum values will be presented using the same number of decimal places as the recorded data. Means, geometric means, and medians will be presented to 1 more decimal place than the recorded data. SD and geometric SD will be presented to 2 more decimal places than the recorded data. The CI about a parameter estimate will be presented using the same number of decimal places as the parameter estimate (i.e. 1 more decimal place than the recorded data). Percentages will be presented to 1 decimal place (e.g. 80.3%).

All data collected will be presented in listings, sorted by vaccine group, site number, subject number, and date/time of the finding if applicable.

The date the first subject signed the informed consent form, the date of the first subject's first visit, the date of the last subject's last visit or last contact, MedDRA version, WHODrug version, and SAS version used for the analysis will be presented for all screened subjects.

7.1.2 Imputation rules

There will be no imputation for missing data with the exception of missing severity, missing relationship, and missing or partial dates (i.e. start and stop dates for AEs). If the severity of an unsolicited adverse event is missing, "severe" will be imputed. If the relationship to a study drug of a solicited or unsolicited adverse event is missing, "related" will be imputed. Partial dates will

be presented as they are in the listings. The partial dates of AEs will be imputed to determine the relationship between the onset of AE and the study drug vaccination date.

The following methods will be used to impute missing or partial dates of the start date of AEs.

Month/year available and day missing:

If the month and year are the same as those in the vaccination date, the vaccination date is to be used to impute the AE start date.

If the month and year are different from the vaccination date, then the first day of the month will be used for the start date given that this does not result in a date prior to the vaccination date. If it would be prior to the vaccination date, the vaccination date is to be used to impute the start date of the AE.

Year available and month/day missing:

If the year is the same as the year of the vaccination date, the vaccination date is to be used to impute the AE start date. If the year is different from the vaccination date, then the start date is to be set as January 1st as long as that this does not result in a date prior to the vaccination date. If it is prior to the vaccination date, the vaccination date is to be used to impute the start date of the AE.

For imputation of partial end dates for AEs and if the AE is not ongoing by the end of the study the following rules (worst case scenario) will be considered: If only the day is missing but the month and year are known, the last day of the month will be used. If the day and month are missing but the year is known, the last day of the year will be used.

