9.1.2 Demographics, Medical History and Prior Medications

Demographic information to be obtained will include date of birth, gender, and race as described by the subject.

Medical History will also be collected, including but not limited to any medical history that may be relevant to subject eligibility for trial participation such as prior vaccinations, concomitant medications, and previous and ongoing illnesses or injuries. Relevant medical history can also include any medical history that contributes to the understanding of an AE that occurs during trial participation, if it represents an exacerbation of an underlying disease/preexisting problem.

All medications (pharmaceutical products only) and vaccines taken or received by the subjects within 4 weeks prior to Day 1 (Month 0), blood products within 3 months prior to Day 1 (Month 0), and immunosuppressive therapy within 6 months prior to Day 1 (Month 0) are to be recorded on the Prior and Concomitant Medications eCRF. The use of antipyretics and/or analgesic medications within 24 hours prior to vaccination must be identified and the reason for their use (prophylaxis versus treatment) must be described in the source documents or the eCRF. Trial vaccination should be delayed if subjects have used antipyretics and/or analgesic medication within 24 hours prior to vaccine administration.

Medications taken for prophylaxis are those intended to prevent the onset of AEs following vaccination. Medications taken for treatment are intended to reduce or eliminate the presence of symptoms that are present.

CONFIDENTIAL

All concomitant therapy taken or received during the period starting with the administration of trial vaccine (Day 1 [Month 0]) and ending one month (minimum of 28 days) after vaccination must be recorded in the subject's source document and eCRF. Additionally, the receipt of any dose of any licensed dengue vaccine should be recorded throughout the trial using the concomitant medication page of the eCRF.

Prohibited Therapies are in Section [7.2](#).

Medical history (including corresponding medication) to be obtained will include any significant conditions or diseases that have disappeared or resolved at or prior to signing of informed consent.

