10.3 Additional Points to Consider for AEs

An untoward occurrence generally may:

- Indicate a new diagnosis or unexpected worsening of a pre-existing condition. Intermittent events for pre-existing conditions or underlying disease should not be considered as AEs.
- Necessitate therapeutic intervention.
- Require an invasive diagnostic procedure.
- Require vaccine discontinuation or a change in concomitant medication.
- Be considered unfavorable by the Investigator for any reason.

Diagnoses *vs.* signs and symptoms:

- Each event should be recorded to represent a single diagnosis. Accompanying signs (including abnormal laboratory values) or symptoms should NOT be recorded as additional AEs. If a diagnosis is unknown, sign(s) or symptom(s) should be recorded appropriately as an AE(s).

Worsening of AEs:

- If the subject experiences a worsening or complication of an AE after starting administration of the investigational vaccine, the worsening or complication should be recorded as a new AE. Investigators should ensure that the AE term recorded captures the change in the condition (e.g., “worsening of...”).
- If the subject experiences a worsening or complication of an AE after any change in investigational vaccine, the worsening or complication should be recorded as a new AE. Investigators should ensure that the AE term recorded captures the change in the condition (e.g., “worsening of...”).

CONFIDENTIAL

Changes in severity of AEs:

- If the subject experiences changes in severity of an AE, the event should be captured once with the maximum severity recorded.
- Preplanned surgeries or procedures:
- Preplanned procedures (surgeries or therapies) that were scheduled prior to signing of informed consent are not considered AEs. Complications resulting from any planned surgery should be reported as AEs.

Elective surgeries or procedures:

- Elective procedures performed where there is no change in the subject's medical condition should not be recorded as AEs, but should be documented in the subject's source documents. Complications resulting from an elective surgery should be reported as AEs.

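### SAP 7.1.2 resets AE onsets recorded in a month or year wholly before vaccination to Day 1, so they count as post-vaccination events

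*SAP*

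**What the plan says.** SAP 7.1.2 gives the purpose of the start-date rules: partial dates are "imputed to determine the relationship between the onset of AE and the study drug vaccination date". Two sets of rules follow.

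- **Day missing, month and year known.** The matching case comes first: "If the month and year are the same as those in the vaccination date, the vaccination date is to be used" as the onset. For any other month, "then the first day of the month will be used for the start date given that this does not result in a date prior" to vaccination. The fallback is: "If it would be prior to the vaccination date, the vaccination date is to be used to impute the start date of the AE".
- **Month and day missing, year known.** The vaccination year is again handled first and set to the vaccination date. Any other year becomes January 1st, with the fallback: "If it is prior to the vaccination date, the vaccination date is to be used to impute the start date of the AE".

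For partial end dates of events that are not ongoing, the same section uses the last day of the known month or year. SAP 7.1.3 makes the vaccination date Study Day 1 and the day before it Day -1. SAP 7.11.1 tabulates unsolicited AEs by onset on Days 1–28, 1–14 and 15–28.

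**The concern.** Setting an uncertain onset to the vaccination date is a reasonable conservative choice, and the same-month and same-year branches make it. The fallback branches are different. By the time they are reached, the part of the date that was recorded already shows that onset came before vaccination. The rule then overrides that information, although its stated purpose is to establish exactly this ordering.

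At stake are the counts of post-vaccination unsolicited AEs, which feed a secondary safety endpoint (the percentage of subjects with unsolicited AEs over 28 days). An event with less date information would be counted, while the same event with a complete date would not.

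**Working it through.** The documents state no figure to reproduce. The check is of the logic of the rule.

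**Inputs.** The month-level and year-level start-date rules and the end-date rule (SAP 7.1.2); the definition of Day 1 (SAP 7.1.3); the onset windows (SAP 7.11.1); 200 subjects per arm (Protocol 2.0).

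**When the month fallback can be reached.** Let v be the vaccination date, in month M, and let m be the recorded month.

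1. If m = M, the first branch applies, so the fallback requires m ≠ M.
2. The fallback also requires the first day of m to be before v.
3. If m were later than M, its first day would be after v, which contradicts step 2. So m is earlier than M.
4. The last day of m is then before the first day of M, which is no later than v. The whole recorded month precedes vaccination.

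The same argument with years in place of months covers the year-only rule.

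**Enumeration.** Both rules were coded as written and run for every vaccination date in 2015–2016 (illustrative dates) against every recorded month and year from 2014 to 2017.

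| Branch | Times reached | Recorded period ended before vaccination |
|---|---|---|
| Month fallback | 17,199 | 17,199 |
| Year fallback | 1,097 | 1,097 |

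The number of partial dates imputed to any day before vaccination was 0. These counts are combinations of dates, not expected AE records. They show that the fallback has no uncertain cases in it, and that under the rule no partly dated AE can be classed as pre-vaccination.

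**Example: vaccination on 20 September 2015 (illustrative).**

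| Recorded onset | Onset used | In the Day 1–28 and Day 1–14 tables? |
|---|---|---|
| 31 August 2015 (full date) | Day -20 | No |
| August 2015 | 20 September 2015 = Day 1 | Yes |
| 2014 | 20 September 2015 = Day 1 | Yes |
| September 2015 | 20 September 2015 = Day 1 (true order unknown) | Yes |
| October 2015 | 1 October 2015 | Yes |

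If the end of the second event is also recorded only as August 2015, the end-date rule gives 31 August. The event then ends 20 days before its imputed start. No text in the SAP checks for this.

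**Size per record.** One affected subject changes a percentage by at most 1/200 = 0.5 percentage points, and by nothing if that subject already counts at the level being tabulated.

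**Effect of removing the fallback.** All 17,199 month-level and 1,097 year-level combinations would be classed as pre-vaccination. Partial dates in the vaccination month or year, and later ones, would not change.

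**The case against.** The strongest reply is that the branch has almost nothing to act on. Protocol 10.1.1 defines an AE as an occurrence in a subject who has been given the vaccine. Unsolicited AEs are collected on diary cards for 28 days from vaccination, and SAE collection starts at vaccination (Protocol 10.4.3). Protocol 12.1 provides logic checks and site queries for inconsistent dates, and a blinded data review follows (Protocol 13.1, SAP 7.1). A record with an earlier month that survives all this may simply be a date error, for which the vaccination date is a cautious repair in keeping with the worst-case rules elsewhere in SAP 7.1.2. This stands as an argument about size. It does not rescue the rule, because the SAP nowhere says that an earlier month is presumed to be an error. It does affect the remedy: automatic exclusion could drop a real post-vaccination event with a mis-entered date.

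A reader might infer more than the documents support:

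- **That the events become vaccine reactions.** Relationship is the investigator's assessment (Protocol 10.2), and SAP 7.1.2 imputes it as related, or an unsolicited AE's severity as severe, only when that field is also missing.
- **That the protocol sends pre-vaccination events to the AE page.** Protocol 10.3 speaks of "worsening or complication of an AE after starting administration of the investigational vaccine", but says only that the worsening is a new AE, which would have its own later onset. Protocol 9.1.2 does include in medical history "any significant conditions or diseases that have disappeared or resolved at or prior to signing of informed consent", but the same section also takes previous and ongoing illnesses. What remains is a narrow gap. Consent may precede Day 1 by up to 28 days (Protocol 9.1.1), and medical history is scheduled only at screening (Protocol Table 2.a), so an illness arising in between has no clearly assigned place.
- **That the effect can be sized from the calendar or from the 2% reporting threshold.** The share of screening days in an earlier month is not a share of AE records. Crossing the threshold in SAP 7.11.1 would need several subjects in one arm with the same term and the same date defect. The documents support no such count.

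**Conclusion.** The point holds as a defect in the written rule. Both fallback sentences in SAP 7.1.2 apply only to onsets already known to precede vaccination. They turn these into Day 1 post-vaccination AEs, contrary to the rule's stated purpose, and can produce a start date after the end date. No other text in the SAP or protocol overrides them.

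The practical effect is probably very small. The number of records cannot be computed from the documents. The ceiling of 0.5 percentage points per affected subject assumes the planned 200 per arm. The rule is the same in both arms, all analyses are descriptive, and the listings keep the partial dates as recorded, so affected events can be traced. The documents do not support reading this as a bias in the comparison of the arms or as misattribution to the vaccine. It is a minor correction, worth making because it is nearly free.

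**What to change.** Replace both fallback sentences in SAP 7.1.2 with:

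> If the recorded month and year (or the year, when the month is missing) are earlier than those of the vaccination date, the record is queried before database lock. If the date is confirmed or unresolved, the onset is classified as pre-vaccination, excluded from the post-vaccination AE summaries, and shown in a separate listing, unless other recorded information shows onset after vaccination.

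Keep the vaccination-date imputation where the known date parts equal those of vaccination. That choice is conservative under real uncertainty and should stay.

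The cost is a short SAP edit, a small code change and a few queries. The downside is a small risk of leaving out a post-vaccination event whose month or year was mis-entered. The query and the separate listing limit that risk.
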